## **7.7. Value Evidence and Outcome**

Three Health-Related Quality-of-Life (HRQoL) assessments will be performed in this study. More details about all patient questionnaires can be found in the SRM. The following assessments will be administered to subjects in different regions based on the availability of translated versions.

### **7.7.1. European Organization for Research and Treatment of Cancer Quality of Life Questionnaire 30-item Core module (EORTC QLQ-C30)**

The EORTC QLQ-C30 is a 30-item questionnaire containing both single- and multi-item measures [Aaronson, 1993]. These include five functional scales (Physical, Role, Cognitive, Emotional, and Social Functioning), three symptom scales (Fatigue, Pain, and Nausea/Vomiting), a Global Health Status/QoL scale, and six single items (Constipation, Diarrhea, Insomnia, Dyspnea, Appetite Loss, and Financial Difficulties). Scores for each scale and single-item measure are averaged and transformed linearly to a score ranging from 0–100. A high score for functional scales and for Global Health Status/QoL represent better functioning ability or HRQoL, whereas a high score for symptom scales and single items represents significant symptomatology [Proskorovsky, 2014].

### **7.7.2. European Organization for Research and Treatment of Cancer Quality of Life Questionnaire 20-item Multiple Myeloma module (EORTC QLQ-MY20)**

The EORTC QLQ-MY20 is a supplement to the QLQ-C30 instrument used in patients with multiple myeloma [Aaronson, 1993; Cocks, 2007]. The module comprises 20

questions that address four myeloma-specific HRQoL domains: Disease Symptoms, Side Effects of Treatment, Future Perspective, and Body Image. Three of the four QLQ-MY20 domains are multi-item scales: Disease Symptoms (includes bone aches or pain, back pain, hip pain, arm or shoulder pain, chest pain, and pain increasing with activity); Side Effects of Treatment (includes drowsiness, thirst, feeling ill, dry mouth, hair loss, upset by hair loss, tingling hands or feet, restlessness/agitation, acid indigestion/heartburn, and burning or sore eyes); and Future Perspective (includes worry about death and health in the future, and thinking about illness). The Body Image scale is a single-item scale that addresses physical attractiveness. As with the QLQ-C30, QLQ-MY20 domain scores are averaged and transformed linearly to a score ranging from 0–100. A high score for Disease Symptoms and Side Effects of Treatment represents a high level of symptomatology or problems, whereas a high score for Future Perspective and Body Image represents better outcomes [Proskorovsky, 2014].

### **7.7.3. Exit Interview**

All subjects in Parts 1 and 2 will participate in an Exit Interview. The Exit Interview will be conducted to further evaluate disease and treatment related symptoms and their associated impacts on function and health-related quality of life. The Exit Interview will be conducted by a trained interviewer via telephone subsequent to the End of Treatment visit. The Exit Interview should be scheduled to be completed within approximately 21 days of the end of treatment visit.

## **8. DATA MANAGEMENT**

- For this study subject data will be entered into GSK defined CRFs, transmitted electronically to GSK or designee and combined with data provided from other sources in a validated data system].
- Management of clinical data will be performed in accordance with applicable GSK standards and data cleaning procedures to ensure the integrity of the data, e.g., removing errors and inconsistencies in the data.
- Adverse events and concomitant medications terms will be coded using MedDRA (Medical Dictionary for Regulatory Activities) and an internal validated medication dictionary, GSKDrug.
- CRFs (including queries and audit trails) will be retained by GSK, and copies will be sent to the investigator to maintain as the investigator copy. Subject initials will not be collected or transmitted to GSK according to GSK policy.

## **9. STATISTICAL CONSIDERATIONS AND DATA ANALYSES**

Statistical considerations and data analysis may be performed separately and/or combined for Part 1 and Part 2.

## **9.1. Hypothesis(es)**

### **9.1.1. Part 1: Dose-Escalation Phase**

No formal statistical hypotheses are being tested in Part 1. Analysis of the data obtained from Part 1 will only utilize descriptive methods.

### **9.1.2. Part 2: Expansion cohort**

The primary goal of Part 2 is to characterize clinical activity of the combination and to detect if meaningful response rate (ORR) can be achieved. Based on historical information [[Lokhorst](#), 2015] and clinical judgement, the null hypothesis has been defined as  $ORR \leq 40\%$ . The alternative hypothesis has been defined as  $ORR \geq 60\%$  based on clinically meaningful improvement of 20%.

In Part 2, treatment-related Grade 4 or higher AEs will be continuously monitored starting from when 5 subjects are dosed. Based on the 11% Grade 4 or higher AEs observed in the FTIH study (BMA117159), it is considered that the combination treatment has unacceptable toxicity if observed treatment-related Grade 4 or higher AEs is significantly higher than 12% at 1-sided alpha of 0.025.

## **9.2. Sample Size Considerations**

### **9.2.1. Part 1: Dose-Escalation Phase**

The total number of subjects to be enrolled into Part 1 will depend on the number of subjects needed to characterize individual dose cohorts. The sample size is not driven by statistical considerations. However, based on assumptions that 2 different dose levels will be tested (up to 6 subjects per dose level) it is anticipated that up to 12 evaluable subjects will be enrolled in Part 1.

### **9.2.2. Part 2: Expansion Cohort**

Sample size for Part 2 is estimated based on hypothesis specified in Section [9.1.2](#) using the Predictive Probability design [[Lee](#), 2008]. Details of sample size calculation are provided in [Appendix 12](#). The optimal design has  $N_{max} = 28$ , type I error rate of 0.10 and power of 80.6%. The expansion cohort may be stopped early for futility if the predicted probability of success is less than 1.5%. If the true ORR is 40%, the expected sample size is 20 and the probability of early termination is 86.1%; if the true ORR is 60%, the expected sample size is 28 and the probability of early termination is 15.6%.

## **9.3. Sample Size Sensitivity**

There is no need to perform sample size sensitivity analysis.

### **9.3.1. Sample Size Re-estimation or Adjustment**

Sample size re-estimation is not planned for this study.

## 9.4. Data Analysis Considerations

### 9.4.1. Analysis Populations

**All Treated Population:** will consist of all subjects who received at least one dose of study drug(s). Safety and clinical activity data will be evaluated based on this population.

**The Pharmacokinetic Population:** This will consist of those subjects in All Treated Subjects Population from whom at least one PK sample is obtained and analyzed.

**DLT Evaluable Population:** will consist of subjects fulfilling the 'All Treated' population criteria during part 1 (Dose Escalation) and are followed up for a 21-day period or withdrawn within 21 days due to an AE meeting the definition of a DLT as defined in Section 4.2.3.1.

**All Evaluable Population:** This is the population used for decision-making at the futility analysis during part 2 (Expansion Cohort). This will be the population for Bayesian predictive adaptive design as defined in Section 9.5.2 and summaries of response if data warrant. In general, subjects are evaluable if they have received at least 1 dose of treatment for both drugs and the time from the first dose to the time of data cut-off is more than 66 days, i.e., reached the time of three planned disease assessments. Details on deriving the evaluable population will be provided in the RAP.

Additional analysis populations may be defined in the Reporting and Analysis Plan (RAP).

## 9.5. Interim Analysis

### 9.5.1. Part 1: Dose Escalation

During dose escalation, no formal interim analysis will be performed. Data will be reviewed through data visualization tools to inform dose escalation decisions. The mTPI design will be utilized to guide dose escalation/de-escalation decisions. More details of the dose escalation procedure are described in Section 4.2.3.1.

After the last cohort of subjects in Part 1 complete the DLT observation period, a formal interim analysis will be performed to support the RP2D decision, except for scenarios where RP2D is clearly defined by the toxicity profile. Data considered to support RP2D decision will include but not be limited to safety, available PK profiles and observed signs of clinical activity. Details of the interim analysis will be provided in the RAP.

### 9.5.2. Part 2: Expansion

Continuous safety monitoring will be conducted for the expansion cohort starting from when 5 subjects are dosed. The observed number of treatment-related Grade 4 or higher AEs will be compared against the safety stopping rule in Table 13. Enrollment may stop if the safety stopping rule is met based on totality of safety data. For example, if there are 3 events out of 5 dosed subjects, enrollment may stop after review of all safety data, if

there is 2 or fewer events out of 5 dosed subjects, enrollment will continue. Operating characteristics for the safety stopping rule are provided in [Appendix 11](#).

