## Statistical Analysis

For part 1, no formal statistical hypotheses are being tested. In Part 1, the dose escalation decisions will be guided by the Modified Toxicity Probability Interval (mTPI) approach, as well as the totality of the safety data. After the last cohort of subjects in Part 1 completes the 21-day DLT observation period, a formal interim analysis will be performed to support the RP2D decision, except for scenarios where RP2D is clearly defined by the toxicity profile.

The primary goal of Part 2 is to confirm safety and to characterize clinical activity of the combination and to detect if meaningful overall response rate (ORR) can be achieved.

During part 2 of the study, treatment-rated Grade 4 or higher AEs will be continuously monitored starting from when 5 subjects are dosed. If observed toxicity level is significantly higher than 12% at 1-sided alpha of 0.025, the study may be terminated early based on totality of safety data. The 12% threshold is chosen based on 11% Grade 4 or higher AE observed in study BMA117159.

For Part 2, futility analyses for ORR will start when 10 subjects are evaluable. Enrollment may stop if the stopping rule is met based on totality of data.

Primary analysis of the data captured in Part 1 and Part 2 will be performed approximately 15 months from the last subject first visit (LSFV) to test the hypothesis that a meaningful response rate (ORR) can be achieved of the combination. Participants may discontinue the study treatment if meaningful response rate (ORR) cannot be achieved. For primary analysis, data may be combined from parts 1 and 2.

Final analysis of the data captured in Part 1 and Part 2 will be undertaken after all subjects meet at least one of the following criteria: have reached the end of study or died. End of study is defined as when all subjects have been followed for 36 months from first dose of study treatment or died or withdrew consent or are lost to follow-up or the safety stopping criteria is met, whichever occurs first.

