**Table 13 Safety Stopping Rules for the Expansion Cohort**

Number of dosed subjects	Stop if treatment related Grade 4 or higher AEs larger or equal to this number
5	3
6-10	4
11-14	5
15-19	6
20-25	7
26-28	8

Interim analyses for ORR will start when at least 10 subjects are evaluable as defined in Section [9.4.1](#). Subjects who initially received RP2D in Part 1 may also be included. The observed number of subjects with unconfirmed response of PR or better will be compared with the stopping boundary in [Table 14](#). Enrolment may stop if the stopping rule is met. Final decision will be based on the totality of data. For example, if there are 2 unconfirmed responses out of 10 evaluable subjects, enrolment may stop after review of all available data; if there are 3 or more unconfirmed responses out of 10 evaluable subjects, enrolment will continue.

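### The Part 2 toxicity rule sets no limit before the fifth dosed subject, although its own limit of 3 could start at the third with no added false alarms (low severity)

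*Protocol*

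**What the plan says.** The synopsis (Statistical Analysis), Section 9.1.2 and Section 9.5.2 agree on the starting point. Section 9.1.2 says that "treatment-related Grade 4 or higher AEs will be continuously monitored starting from when 5 subjects are dosed", and Section 9.5.2 repeats it: "Continuous safety monitoring will be conducted for the expansion cohort starting from when 5 subjects are dosed".

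The criterion for unacceptable toxicity is also in Section 9.1.2: an observed rate "significantly higher than 12% at 1-sided alpha of 0.025". The 12% is set just above the 11% seen in the first-in-human study.

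Table 13 ("Safety Stopping Rules for the Expansion Cohort") turns this into counts: 3 at 5 dosed subjects, 4 at 6–10, 5 at 11–14, 6 at 15–19, 7 at 20–25 and 8 at 26–28. It has no row below 5. The rule is advisory: reaching a limit leads to a review of all safety data, after which enrolment may stop.

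**The concern.** The criterion is a significance statement that does not depend on having five subjects. If the first three expansion subjects all have a treatment-related Grade 4 or higher event, the evidence against 12% is stronger than at 3 of 5, yet only 3 of 5 reaches a limit. The weaker signal prompts the review and the stronger one does not.

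This is the first clinical study of the combination (Section 4.4), so one or two subjects could be dosed after the protocol's own definition of unacceptable toxicity has been met. The usual reason for delaying a first look is to avoid false alarms from very small numbers. The question is whether that reason applies to the limit of 3.

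**Working it through.** **Inputs.** Reference rate 12% and one-sided 0.025 (Section 9.1.2); limits for 5 to 28 dosed subjects (Table 13); maximum of 28 subjects (Section 4.2.3.2). I count each subject at most once.

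**Step 1: reproduce Table 13.** For each n, take the smallest r with P(X ≥ r | n, 0.12) ≤ 0.025, X binomial. All 24 sample sizes from 5 to 28 match the table. With 11% instead, seven do not (6, 15, 16, 20, 21, 26, 27). The rule behind the table is therefore the exact binomial test at 12%.

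**Step 2: apply the same test below 5.**

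- 3 of 3: 0.12³ = 0.0017
- 3 or more of 4: 4 × 0.12³ × 0.88 + 0.12⁴ = 0.00608 + 0.00021 = 0.0063
- 3 or more of 5 (the plan's first limit): 10 × 0.12³ × 0.88² + 5 × 0.12⁴ × 0.88 + 0.12⁵ = 0.01338 + 0.00091 + 0.00002 = 0.0143
- 2 of 2: 0.12² = 0.0144
- 2 or more of 3: 0.0397, not significant

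The plan's criterion thus gives a limit of 3 at both n = 3 and n = 4.

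**Step 3: false alarms.** The third event falls on subject n with probability C(n−1, 2) p³ (1−p)ⁿ⁻³. At p = 0.12:

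- n = 3: 0.00173
- n = 4: 3 × 0.00173 × 0.88 = 0.00456
- n = 5: 6 × 0.00173 × 0.7744 = 0.00803

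The sum is 0.0143, exactly the chance of reaching the limit at n = 5 under the present table. Starting at 3 redistributes that probability over three looks and adds nothing. Listing all 32 outcome sequences of the first five subjects confirms it: none has 3 events by subject 3 or 4 and fewer than 3 at subject 5.

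**Step 4: whole cohort.** An exact subject-by-subject recursion to n = 28, removing sequences as they reach a limit, gives:

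| True rate | Ever crossing, start at 5 | Ever crossing, start at 3 | 3 or more events in first 4 | Expected dosed, start at 5 | Expected dosed, start at 3 |
|---|---|---|---|---|---|
| 12% | 5.58% | 5.58% | 0.6% | 27.139 | 27.131 |
| 30% | 73.9% | 73.9% | 8.4% | 16.933 | 16.823 |
| 40% | 95.4% | 95.4% | 17.9% | 11.213 | 10.970 |

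The expected saving is 2p³ + 3p³(1−p), two subjects if the limit is met at n = 3 and one if at n = 4: 0.008 at 12%, 0.111 at 30% and 0.243 at 40%.

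**Step 5: a start at 2.** Adding 2 of 2 as a limit raises the crossing probability at 12% from 5.58% to 6.37%. That look is not free.

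**The case against.** A reader might infer that early events would trigger nothing at all, or that the protocol contradicts itself. The documents support neither. All the relevant places start at 5, so this is a consistent design choice. Outside Table 13, SAEs reach the sponsor within 24 hours (Section 7.3.1.7), urgent safety measures apply (10.3), the sponsor may suspend the study at any time (10.6), an internal safety committee reviews data under its own charter (10.9.1), and subject-level toxicity rules operate (6.5). What remains is narrower: the protocol attaches no cohort count for Part 2 to any of these.

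Several further objections limit the size of the point:

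- The expansion opens only after Part 1 has supported a dose, so true rates of 40% are among the less plausible. The 21-day DLT window cannot exclude later toxicity.
- Counts can fall. Appendix 7 lets the investigator revise causality, so 3 related events at subject 3 could become 2 by subject 5. The equality in Step 3 holds only under fixed attribution.
- Section 9.5.2 sets no waiting period between expansion subjects. If enrolment overlaps, subjects 4 and 5 may already be dosed when the third event appears, so the savings above are upper bounds.
- The criterion is also met at 2 of 2, so where to start remains a judgement. That is fair, but 2 of 2 costs extra false alarms and 3 of 3 does not.

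The operating characteristics in Appendix 11 are not in the text at hand, so the sponsor's own figures could not be compared. None of these objections identifies a real cost of starting at 3.

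**Conclusion.** The point stands as a free improvement of low severity. Table 13 omits two sample sizes at which the protocol's own criterion already gives a limit of 3, and including them changes neither the false-alarm nor the detection probability. The benefit is at most one or two subjects in trials with three or more early events, and a small fraction of a subject on average.

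The equality rests on fixed causality attribution and on the comparison at n = 5 actually being made. The second condition matters because the limit of 3 applies at that one sample size only: at 6 subjects it becomes 4, since 3 or more of 6 has p = 0.0261.

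**What to change.** In the synopsis, Section 9.1.2 and Section 9.5.2, change the start of monitoring from 5 to 3 dosed subjects. In Table 13, let the first row cover 3–5 dosed subjects with the limit of 3. Keep all other rows and the advisory review of the totality of safety data. Do not add a limit at 2 of 2.

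The cost is wording in three places and one table cell. Under the assumptions above, false-alarm rate, detection rate and maximum sample size do not change.

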**Table 13 Safety Stopping Rules for the Expansion Cohort**

Number of dosed subjects	Stop if treatment related Grade 4 or higher AEs larger or equal to this number
5	3
6-10	4
11-14	5
15-19	6
20-25	7
26-28	8

Interim analyses for ORR will start when at least 10 subjects are evaluable as defined in Section [9.4.1](#). Subjects who initially received RP2D in Part 1 may also be included. The observed number of subjects with unconfirmed response of PR or better will be compared with the stopping boundary in [Table 14](#). Enrolment may stop if the stopping rule is met. Final decision will be based on the totality of data. For example, if there are 2 unconfirmed responses out of 10 evaluable subjects, enrolment may stop after review of all available data; if there are 3 or more unconfirmed responses out of 10 evaluable subjects, enrolment will continue.

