### **4.4. Design Justification**

This is the first clinical study in which belantamab mafodotin will be administered in combination with pembrolizumab. Therefore, a two-part study design is implemented to allow for careful safety assessments during dose escalation. Part 1 will consist of dose escalation to establish the RP2D of belantamab mafodotin in combination with 200 mg of pembrolizumab. Once RP2D has been established, Part 2 will enroll an additional 28 subjects with RRMM to further confirm safety and to assess the clinical activity of the

combination at the RP2D of belantamab mafodotin. Futility analyses will be conducted from when response data is available from 10 subjects. Details of the futility analysis are described in Section 9.5.2.

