**12.11. Appendix 11: Operating Characteristics of Safety Stopping Rule for Expansion Cohort**

## 12.12. Appendix 12: Sample Size Calculation for the Expansion Cohort

Sample size is calculated using the Predictive Probability Design for Phase II studies software. The optimal design is identified by specifying interim looks starting from a minimum of 10 evaluable subjects, “maximizing power under the alternative hypothesis” as the optimizing criterion, Theta\_L(threshold of early futility stopping)/Theta\_U(threshold of early efficacy stopping)/Theta\_T(threshold) as default, a weakly informative beta prior Beta (0.04, 0.06) representing information from 0.1 subject with a mean response of 40%, type I error rate controlled at 0.10, and power of 80%. The design with smallest  $N_{max}$  that controls the type I and type II error rate is the optimal design.

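### Counting Part 1 RP2D subjects in the futility looks detaches Table 14 from the stated 1.5% rule, because its limits hold only for a final total of 28

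*Protocol*

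**What the plan says.** Section 9.2.2 sizes Part 2 with a predictive probability design: a maximum of 28 subjects, "type I error rate of 0.10 and power of 80.6"%. It says the cohort "may be stopped early for futility if the predicted probability of success is less than 1.5"%. The stated consequences are "If the true ORR is 40%, the expected sample size is 20 and the probability of early termination is 86.1"%, and "if the true ORR is 60%, the expected sample size is 28 and the probability of early termination is 15.6"%. Appendix 12 gives the prior as "a weakly informative beta prior Beta (0.04, 0.06").

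Section 9.5.2 carries this out. "Interim analyses for ORR will start when at least 10 subjects are evaluable", and the response count is compared with Table 14, which has a row for every number of evaluable subjects from 10 to 28. The same paragraph adds: "Subjects who initially received RP2D in Part 1 may also be included". It also makes the limits non-binding, leaving the decision to the totality of data.

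On size, section 4.4 says "Part 2 will enroll an additional 28 subjects with RRMM". Sections 4.1 and 4.3 give up to 12 subjects in Part 1 and 28 in Part 2. Section 4.2.3 requires at least 3 evaluable subjects per dose level, and section 9.2.1 plans up to 6. Section 9.6 lets the primary analysis treat the two parts separately or combined.

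**The concern.** A predictive-probability limit depends on how many subjects are still to come. Table 14 is computed as if the trial ends at subject 28. If 3 to 6 of the subjects counted come from Part 1 and Part 2 still enrols 28, then subject 27 in the count is not the second to last: 4 to 7 Part 2 subjects remain. A count that is hopeless with one subject left may not be hopeless with seven left.

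At stake is a wrong stop for futility. Enrolment into an active combination could end while the chance of success is many times the 1.5% that section 9.2.2 gives as the threshold. The power in that section would also not describe the rule being run.

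**Working it through.** **Inputs.** Null ORR 0.40, alternative 0.60, maximum 28, threshold 1.5% (9.1.2, 9.2.2); prior Beta(0.04, 0.06), first look at 10, then after every subject (Appendix 12); limits from Table 14. The protocol prints no success cut-off. Table 14's last row (stop at 14 or fewer of 28) implies success at 15 or more. Subjects carried over: k = 3 to 6.

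**Step 1: reproduce the plan.** With x responses in n, final size N and cut-off r, the predictive probability is

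PP = Σ C(N−n, j) · B(0.04+x+j, 0.06+N−x−j) / B(0.04+x, 0.06+n−x), summed over j from r−x to N−n.

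With N = 28 and r = 15, every limit from n = 10 to 27 is the largest count with PP below 1.5%. Examples:
- n = 11: PP is 0.12% at 2 responses and 1.51% at 3.
- n = 17: PP is 1.30% at 6 and 7.86% at 7.
- From n = 23 on, PP at the limit is exactly 0, because 15 is out of reach (9+5, 10+4, …, 13+1 all equal 14).

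An exact binomial recursion over rows 10 to 27 gives type I error 0.0997, power 80.55%, and early termination 86.1% (ORR 40%) and 15.5% (ORR 60%). This matches 9.2.2 to rounding, so the table is specific to a total of 28.

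**Step 2: predictive probability at the limit with k carried over, final test of at least 15 of 28 in Part 2 alone.** Values are averaged over how the responses split between Part 1 and Part 2 (hypergeometric weights).

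| Pooled count at limit | k = 3 | k = 6 |
|---|---|---|
| 7/20 | 1.4% | 3.4% |
| 9/22 | 5.7% | 9.8% |
| 11/25 | 8.2% | 14.2% |
| 13/27 | 22.6% | 29.0% |
| 14/28 | 34.4% | 38.7% |

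Weighting only by response sequences that passed every earlier look lowers the 13/27 averages to about 20% and 25%, still far above 1.5%.

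Single paths vary widely. Take k = 6 with 2 Part 1 responders and 14/28 pooled. Part 2 stands at 12/22 and needs 3 of its last 6: PP = 64%, and P(Bin(6, 0.6) ≥ 3) = 82%. With 3 Part 1 responders, PP is 36%.

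**Step 3: predictive probability at 13/27 with a pooled final test.** The cut-off is not stated, so a range is needed. For a total of 31, PP is 6.6% with cut-off 17 and 29.8% with cut-off 16. For a total of 34, it is 22.4% with cut-off 18 and 46.3% with cut-off 17. The range is about 7% to 46%.

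**Step 4: power at ORR 60%, limits followed.** The recursion keeps Part 1 and Part 2 responses separate and compares their sum with Table 14.

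| Final test on Part 2 only, ≥15/28 | k = 3 | k = 4 | k = 5 | k = 6 |
|---|---|---|---|---|
| Looks through row 27 | 77.5% | 76.8% | 76.2% | 75.6% |
| Row 28 also used as a stop | 75.9% | 75.1% | 74.4% | 73.7% |

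Type I error in these eight cases runs from 0.078 down to 0.055. With a pooled final test, power runs from 75.6% (18/33, row 28 used) to 83.3% (17/34, looks through row 27). The top of that range has type I error 0.105. If carried-over subjects count toward a total of 28 in both the looks and the test, power stays 80.55%.

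The probability of crossing a limit through row 27 stays at 15.5% and 86.1% whatever k is, because it depends only on the pooled sequence.

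**The case against.** The strongest reply is that the protocol leaves room for the rule to do no harm. Including Part 1 subjects is optional and the limits are non-binding. Section 9.8.1 uses the same All Evaluable population at the futility look and the primary analysis, and pooling is allowed, so the final test may be pooled too. Section 4.2.3.2 speaks of up to 28 subjects, which could be read as a cap that includes those carried over. Evaluability takes more than 66 days from first dose, so by pooled subject 27 the last Part 2 subjects may already be enrolled. Moreover, the looks count unconfirmed responses while the endpoint needs confirmation, and the recursion treats the two as one event.

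Most of this stands as a limit on the size of the effect. It does not remove the fault. No passage says that carried-over subjects reduce Part 2 enrolment, and section 4.4 points the other way. Pooling the final test still leaves the predictive probability at 13/27 well above 1.5%. Discretion to override a table does not make its limits correct.

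Two stronger readings are tempting. A reader might infer that power simply drops to 74% to 76%. That needs binding limits, row 28 used as an interim stop and a Part 2-only final test, and the protocol fixes none of these. A reader might also infer that early stopping at ORR 60% rises from 15.6% to 19.4%. The 19.4% adds row 28 (1 − 0.8055), which the 15.6% leaves out, so the two are not like for like.

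**Conclusion.** The point holds as an internal inconsistency with conditional consequences. Table 14 carries out the 1.5% rule only for 28 subjects in total, yet section 9.5.2 admits extra subjects without adjusting it.

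If 3 to 6 Part 1 subjects are counted in addition to 28 in Part 2, late stops can occur at average predictive probabilities of about 23% to 29% at 13/27 (Part 2-only test), or about 7% to 46% (pooled test, depending on cut-off). Power at ORR 60% with a Part 2-only test and looks through row 27 is about 77.5% to 75.6%, against 80.6% stated; with row 28 as a stop it is 75.9% to 73.7%. With a pooled test it is about 76% to 83%. All these power figures assume that the limits are followed. There is no loss if carried-over subjects count toward the 28.

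With a Part 2-only test the error is conservative for type I error, so the risk is a wrongly abandoned combination, not a false claim. It would also be too strong to say that success is still likely at a stop: that is true of some paths but not of the average.

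**What to change.** Preferred: in section 9.5.2, delete the sentence on Part 1 RP2D subjects and state that Table 14 applies to Part 2 evaluable subjects only. This restores the stated operating characteristics. The cost is that the first look comes 3 to 6 evaluable subjects later.

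If Part 1 subjects are to count, choose one of these now:
- State that they count toward the total of 28 in both the looks and the final test. Table 14 and section 9.2.2 then stand, and fewer new Part 2 subjects are enrolled, so section 4.4 needs the matching change.
- Keep 28 new Part 2 subjects, fix the number carried over, and recompute Table 14, the final cut-off, power, type I error and early-termination probabilities for a maximum of 28 plus that number. This is one rerun of the design software.

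Under either alternative, section 9.6 should say which subjects form the final ORR test.
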